Anxiety will be assessed by the Hospital Anxiety and Depression Scale (HADS), the State-Trait Anxiety Inventory (STAI) and the Hamilton anxiety scales. The HADS will serve as a primary outcome measure. Depression will be assessed with the HADS and the Hamilton Depression Rating Scale (HAM-D). Daily pain levels will be assessed throughout the study. The researchers will also assess participant quality of life with the European Organization for Research and Treatment of Cancer Quality of Life Questionnaire (EORTC-QLQ), feelings about life purpose and spirituality with the Functional Assessment of Chronic Illness Therapy-spirituality (FACIT-Sp), and spirituality in relation to the self with the Self-Expansiveness Level Form (SELF). The researchers will assess natural killer (NK) cell activity through diagnostic flow cytometry, assessing blood drawn at baseline, on the morning of the day after each psilocybin-assisted session and two weeks after the second psilocybin session. The researchers will assess the nature and extent of psilocybin effects related to producing a mystical or peak experience through the States of Consciousness Questionnaire, administered 24 hours after each experimental session.

Ethics

The trial will not be initiated until appropriate Institutional Review Board (IRB) approval of the protocol and the informed consent document has been obtained. In addition, all documents will be submitted to other authorities in compliance with local jurisdictions. The IRB and, if applicable, other authorities must be informed of protocol amendments in accordance with local legal requirements.

This trial will be conducted in accordance with the most recently acceptable version of the Declaration of Helsinki, Good Clinical Practice (GCP) according to International Conference on Harmonisation (ICH) guidelines, and applicable standard operating procedures (SOPs). The trial will be conducted under a protocol reviewed and approved by an IRB; the trial will be conducted by scientifically and medically qualified persons; the benefits of the study are in proportion to the risks; the rights and welfare of the subjects will be respected; the physicians conducting the trial do not find the hazards to outweigh the potential benefits; each subject, or where applicable, each subject's legally acceptable representative(s) will give his or her written informed consent before any protocol-driven tests or evaluations are performed.

Informed Consent of Subject

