The secondary objectives of this study include assessing depression, spirituality, quality of life, perceived self-boundaries, pain and natural killer (NK) cell activity in participants, and examining possible relationships between measures of the psilocybin experience and anxiety and spiritual beliefs.

Depression: We will assess the effects of psilocybin-assisted psychotherapy on symptoms of depression. Changes in depression will be assessed via clinician-administered and self-report instruments at baseline and two weeks after the second psilocybin-assisted session. When applicable, changes in depression will be assessed two weeks after the second open-label session and two months after the second open label or experimental session.

Quality of Life, Beliefs about Spirituality and Self-Boundaries: We will investigate the effects of psilocybin-assisted psychotherapy on beliefs about life purpose, spirituality, self-boundary and quality of life. Changes in spiritual beliefs and quality of life will be assessed via self-report measures at baseline and two weeks after the second psilocybin session. When applicable, changes in spiritual

beliefs and quality of life will be assessed two weeks after the second open-label session and two months after the second open label or experimental session.

Pain: A third secondary objective is to learn whether psilocybin-assisted psychotherapy produces at least transient changes, as analgesia or reduction in physical pain. Changes in pain will be assessed via daily diaries using visual analog scales and via daily diaries of medication use. When applicable, changes in pain will be assessed two weeks after the second open-label session and on the day two months after the second open label or experimental session.

Immune function: We wish to investigate the short-term and continued effects of psilocybin-assisted therapy on immune system function. Changes in immunological function will be assessed by NK cell counts made at baseline, 24 hours after each experimental session and two weeks after the second psilocybin-assisted session. When applicable, NK cell counts will occur 24 hours after each open-label session and two weeks after the second open-label session.

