All outcome measures selected for this study were chosen because they are well-recognized in the literature and because they are or will be used in related pilot studies, allowing comparison across these investigations. The primary outcome measure for this study will be the HADS anxiety score. The investigators will also measure anxiety with the STAI and the HAM-A. The investigators will assess depression with HADS depression scores and with the HAM-D. Participant beliefs about life purpose and spirituality will be measured with the FACIT-Sp, spirituality in relation to self-concept by the SELF, and quality of life will be assessed with the EORTC-QLQ-C15. Daily pain levels will be assessed via participant response on a visual analog scale, and daily pain and anxiety medication use will serve as an indirect measure of anxiety and experienced pain. Natural killer cell counts will serve as a measure of innate immune system function.

All participants will be screened via SCID and HADS, as described above in “Screening”. The investigators will also use MMSE scores to assess study eligibility and mental competence throughout the course of the study.

The SCQ will serve as a process measure, assessing presence and degree of effects of psilocybin, and the SELF will serve as a process measure of self-boundary change. The KRPS, a measure frequently employed in studies of people with cancer, will serve as a means of rating performance status.

Table 1: List of assessments for use in this study. Time listed in minutes.

Assessment	Abbreviation	Measure of	Time needed	Clinician rated	Participant Self-rated	Purpose of Assessment/Measure
Daily Medication Diary	--	Anxiolytic & pain management meds	5 min		X	Outcome
Daily Pain Level Diary	--	Daily pain levels	5 min.		X	Outcome
Europ. Organiz. For Research and Treatment of Cancer; Quality of Life Questionnaire-C15	EORTC QLQ-C15	Global quality of life	5-10 minutes.		X	Outcome
Functional Assessment of Chronic Illness Therapy-spirituality	FACIT-Sp	Spiritual or life purpose beliefs	5 min.		X	Outcome
Hamilton Anxiety Rating Scale	HAM-A	Anxiety	5-10 min	X		Outcome
Hamilton Depression Rating Scale	HAM-D	Depression	5-10 min	X		Outcome
Hospital Anxiety and Depression Scale#	HADS	Anxiety + Depression	5-10 min.		X	Screening & Outcome
Karnofsky Performance R__ Scale	KPRS	Everyday life function	5 minutes	X		Supplemental
Mini Mental State Examination	MMSE	Mental status / competency	15 minutes	X		Screening, continued eligibility

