Introductory psychotherapy sessions will be recorded to audio and video. No identifying information save assigned participant subject number will be written on any session recordings. Participants will have an opportunity to review session recordings.

Assessment

Participants will undergo assessment with MMSE to ensure their continued eligibility prior to each introductory psychotherapy session. They will complete the HADS and STAI prior to the first introductory session, and the FACIT-SP and EORTC-QLQ-C15 prior to the second introductory session. They will complete daily pain and medication diaries during this time period.

Psilocybin-Assisted Psychotherapy (Visit #5, Visit #8)

Psychotherapy

There will be two psilocybin-assisted psychotherapy sessions scheduled to occur seven to fourteen (14) days apart, on study visits #5 and #8. Both psilocybin-assisted psychotherapy sessions will take place at the study site and will be staffed by the two investigator-therapists, one male and one female. Procedures for the two drug-assisted sessions will be identical. During the second experimental session, the participant and therapist-investigators may discuss material or experiences from the first psilocybin-assisted session.

Participants will arrive at the Cancer Center at approximately 9:00 AM. Participants will be instructed to refrain from alcoholic beverages starting 12:00 on the night prior to each psilocybin-assisted session, and to eat only a light breakfast on the morning of the

session. On arrival, they will have a blood draw for the assessment of liver function and metabolism, and they will have urinary drug and pregnancy screens. After undergoing these screens, one of the investigators will conduct the MMSE, and the participant will complete outcome measures. He or she may return completed daily pain and medication diaries at this point. Results from laboratory tests will be available approximately 45 minutes after the blood draw, and significantly abnormal results will result in rescheduling of psilocybin session or withdrawing the subject from the study. Positive pregnancy screen will result in withdrawal from the study.

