The participant and therapists will continue to work with material from the first psilocybin-assisted session and will discuss ways in which the participant has integrated this material into his or her everyday life. There will also be more explicit preparation for the second psilocybin session, including discussing any changes or elaborations in plans or goals and addressing participant concerns raised during the first session. They will review hypnotic induction and mindfulness techniques during this interim non-drug psychotherapy session.

Assessment

On the morning of the day after each psilocybin-assisted session, participants will complete the SELF and the SCQ prior to undergoing integrative psychotherapy. They will also undergo a blood draw for the assessment of natural killer (NK) cell numbers on the morning of the day after each psilocybin-assisted session. Prior to integrative psychotherapy scheduled between the first and the second psilocybin-assisted psychotherapy session, participants will be assessed for continued study eligibility with MMSE. After undergoing the MMSE, participants will be assessed for anxiety and depression with the HADS, STAI, HAM-A and HAM-D, and they will be assessed for spirituality and quality of life with the FACIT-Sp and EORTC-QLQ-C15.

Final Evaluation in Randomized Phase (Visit #10)

Psychotherapy

Psychotherapy will not be conducted during the evaluation and assessment occurring two weeks after the second psilocybin-assisted session.

Assessment

Two weeks after the second psilocybin-assisted psychotherapy session, participants and a primary caregiver will arrive at the cancer center. Participants will undergo a comprehensive evaluation, including administration of KPRS, MMSE, HAM-A and HAM-D, STAI, FACIT-Sp, EORTC-QLQ and SELF. Participants and primary caregivers will complete the HADS. After this evaluation, participants will briefly meet with the investigators and the study blind will be broken, as described below.

Participants will complete the Reactions to Research Participation Questionnaire (RRPQ), an instrument examining reasons and feelings related to taking part in research studies, including reasons for taking part in the study and positive and negative feelings related to research participation.

Unblinding and Opportunity to Enter the Open-Label Study Segment or Two-Month Follow-up (Visit 10)

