The sponsor or the investigator (following consultation with the sponsor) has the right to discontinue this study at any time. If the trial is prematurely terminated, the investigator is to promptly inform the study subjects and she or he should assure appropriate therapy and follow-up. If the trial or study is prematurely discontinued, all procedures and requirements pertaining to the archiving of the documents will be observed. All other study materials will be returned to the sponsor, will be treated in accordance with federal and local regulations. DEA requires destruction of unused schedule 1 drugs in studies.

Data Analysis

The primary analyses for this study will be a repeated measures analysis of variance (ANOVA) with condition (active placebo versus experimental dose) as a between-subject

factor and time of administration (baseline versus two weeks after the second experimental psilocybin-assisted session) as a repeated measure. The investigators will employ separate repeated measures ANOVAs to examine the effects of psilocybin-assisted psychotherapy on all outcome variables, including the primary outcome variable. Separate analyses will be performed for HADS, HAM-A and STAI anxiety scores, HADS and HAM-D depression scores, EORTC-QLQ-C15 scores, FACIT-Sp scores and NK cell counts. The investigators will perform post-hoc tests (as Tukey's test) on any statistically significant interactions. Probability of rejecting the null hypothesis will be set at 0.05. Because of the pilot nature of this study and small sample size, we will not employ Bonferroni corrections for when examining analyses results for measures of anxiety. In the case of pain levels measured by daily diary, the investigators will perform two repeated measures ANOVAs comparing average pain levels at baseline versus average pain levels for the weeks immediately after the first and after the second experimental sessions, with p. set at 0.05. The investigators are interested in discovering whether there are differences in pain level between active placebo and experimental dose participants immediately after undergoing psilocybin-assisted psychotherapy.

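### The 24-hour NK cell counts, the only data on the short-term immune objective, enter no planned comparison between conditions or with baseline

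*Protocol*

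**What the plan says.** - **Objective.** The Immune function paragraph of Secondary Objectives states: "We wish to investigate the short-term and continued effects of psilocybin-assisted therapy on immune system function". It names as its data "NK cell counts made at baseline, 24 hours after each experimental session and two weeks after the second psilocybin-assisted session".
- **Sampling.** The Time and Events table marks the NK count at V3, V6, V9 and V10, and not on the dosing days V5 and V8.
- **Analysis.** Data Analysis specifies a repeated measures ANOVA with condition as the between-subject factor and "time of administration (baseline versus two weeks after the second experimental psilocybin-assisted session) as a repeated measure". NK cell counts are listed by name among the outcomes analysed this way. Pain is handled differently: it gets two further ANOVAs, comparing baseline with the week after each session.
- **Other use of the 24-hour samples.** Later in Data Analysis, the investigators may relate SCQ scores to NK counts from blood taken about 23 hours after each session.
- **Terms.** The Summary says "The researchers will assess natural killer (NK) cell activity through diagnostic flow cytometry", and the opening sentence of Secondary Objectives refers to "perceived self-boundaries, pain and natural killer (NK) cell activity in participants". Assessments and Measures says "Natural killer cell counts will serve as a measure of innate immune system function", and the Assessment text for the integrative sessions says "They will also undergo a blood draw for the assessment of natural killer (NK) cell numbers".

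**The concern.** The objective has two time horizons, and the blood sampling serves both. The analysis serves one. V6 and V9 are the only samples that bear on a short-term effect, and the time factor excludes them. The post-hoc tests do not bring them back, because those tests follow interactions in the same two-level model.

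This is not a detail that the protocol leaves open for a statistical analysis plan. It fixes the levels of the time factor and assigns NK counts to them. The pain paragraph shows that the authors wrote a short-term comparison where they wanted one.

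At stake is a secondary objective. Participants with a life expectancy of one year or less give two blood samples for a question that no planned comparison addresses. Any 24-hour result by dose would then be an unplanned comparison.

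**Working it through.** **1. Samples against analyses.**

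| Visit | Approximate study day | NK drawn | In the NK ANOVA | Other stated use |
|---|---|---|---|---|
| V3 | 0 | yes | yes (baseline) | none |
| V5 (session 1) | 14 | no | – | – |
| V6 | 15 | yes | no | optional, with SCQ |
| V8 (session 2) | 29 | no | – | – |
| V9 | 30 | yes | no | optional, with SCQ |
| V10 | 43 | yes | yes (two weeks) | none |

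With nine completers there are 9 × 4 = 36 randomised-phase samples. Of these, 9 × 2 = 18 are 24-hour samples outside the ANOVA. The SCQ association concerns the mystical experience, not the dose, so even if carried out it does not estimate a short-term effect of condition.

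**2. Distance from the baseline sample** (days from Time and Events).
- V3 to V6: 15 − 0 = 15 days.
- V3 to V9: 30 − 0 = 30 days, an interval that includes session 1. If the stated 7 to 14 days between sessions is applied to V5 on day 14, V8 falls on days 21 to 28 and V9 on days 22 to 29, so the interval is 22 to 29 days.
- From a hypothetical V5 pre-dose sample: 15 − 14 = 1 day to V6, but 30 − 14 = 16 days to V9, still including session 1.

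**3. Power of a 24-hour contrast.** The protocol gives no power figure for NK. Its general figure, in Statistical Power, is 0.1143 for a two-sample t-test of six versus three at effect size 0.6. With two time points, the condition-by-time test is a two-sample t-test on the change, so the same calculation applies.
- Noncentrality = d / √(1/n₁ + 1/n₂) = 0.6 / √(1/6 + 1/3) = 0.849, with 6 + 3 − 2 = 7 degrees of freedom.
- Exact noncentral-t power at two-sided 0.05 (sidedness is not stated, but two-sided reproduces the plan) = 0.1143. The plan's figure is reproduced.
- This takes 0.6 in standard deviations of the change. If 0.6 is in standard deviations of a single measurement, the standardised change is 0.6 / √(2(1 − ρ)), where ρ is the correlation between baseline and follow-up. The protocol gives no ρ, so these values are assumptions:

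| Assumed ρ | Power |
|---|---|
| 0.3 | 0.096 |
| 0.5 | 0.114 |
| 0.7 | 0.158 |
| 0.9 | 0.374 |

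**4. Multiplicity.** Adding two 24-hour tests to the two-week test, each at 0.05, gives 1 − 0.95³ = 0.143 for at least one false positive if the tests are independent. These tests share participants and a baseline, so independence is a simplification.

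**The case against.** The case against has four parts.

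**Small consequence.** NK count is one of several secondary outcomes in a nine-person pilot that declares its own power very low. No primary or safety conclusion rests on it. This stands. It argues for estimation rather than more tests, but not for leaving the contrast out.

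**The samples are not wholly unused.** The SCQ association is provided for, and nothing forbids describing the 24-hour counts by arm. This stands in part: it would be wrong to say that the samples have no stated use. The association is optional, however, and answers a different question.

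**Baseline timing.** A reader might infer that a V3 baseline invalidates the 24-hour comparison, since V3 precedes the preparatory psychotherapy and has no stated clock time, while the post-session visits are at about 9:00 AM. A pre-dose draw already exists at V5 and V8: "On arrival, they will have a blood draw for the assessment of liver function and metabolism". The documents do not support that inference for the comparison of conditions. Both randomised arms share the V3 baseline, the visit schedule and the psychotherapy, so the distance adds noise and room for chance imbalance at six versus three, not systematic bias. A sample before any therapy is also a defensible reference for an objective about psilocybin-assisted therapy as a package. What stands is that change within an arm cannot be read as the effect of a session alone.

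**Activity versus count.** A reader might infer that the wrong quantity is measured. The Immune function paragraph, Assessments and Measures, Data Analysis and Appendix A all say count, and the integrative-session text says numbers. Activity appears in the Summary and in one introductory sentence. This is an inconsistency of wording.

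**Conclusion.** The point holds as a break between objective and analysis. The protocol asks for short-term immune effects and collects the samples. It then fixes an NK analysis that leaves out 18 of 36 of them, with only an optional association to use them. This follows from the text and needs no assumption beyond nine completers.

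Its importance is modest. A 24-hour contrast would have about 11% power at a standardised change of 0.6, and 10% to 37% over the assumed correlations if 0.6 refers to a single measurement. The gain is therefore a pre-stated estimate, not a decisive test. The documents do not support the stronger conclusions that the baseline biases the comparison of arms or that it must move to V5. A V5 reference would still leave 16 days and all of session 1 before V9. The change is worth making because it uses samples already planned.

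**What to change.** 1. In Data Analysis, add a sentence for NK cell counts parallel to the one for pain: condition-by-time contrasts of baseline versus V6 and baseline versus V9 as the short-term effect, keeping baseline versus V10 as the continued effect.
2. Report the two 24-hour contrasts as estimates with confidence intervals, or descriptively by arm, rather than as further tests at 0.05.
3. State with the results that V3 lies 15 days before V6 and 30 days before V9 by the schedule, that the V3-to-V9 change also includes session 1, and that within-arm change should be read accordingly.
4. Replace NK cell activity with NK cell count in the Summary and in the opening sentence of Secondary Objectives.

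The cost is a few sentences of protocol text, with no extra visit, blood draw or assay. Taking the baseline tube at V5 instead of V3 is an option the sponsor may weigh. It would shorten the interval to V6 to one day but give up the sample taken before any therapy. Keeping V3 and adding V5 would cost one more assay per participant.

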After giving written consent, participants will be screened for presence of anxiety and for the presence of any psychiatric conditions that preclude study participation, such as psychosis. The principal investigator will conduct the screening evaluation in his office. The Structured Diagnostic Clinical Interview (SCID) will be used for diagnosing anxiety and detecting any conditions that preclude study participation, and the Mini Mental State Evaluation (MMSE) will be used to determine mental state and competency to take part in the study. Only participants with MMSE scores of 27 or higher will be eligible for study participation. The Hospital Anxiety and Depression Scale (HADS) will be used to quantify anxiety. Only people who are diagnosed with anxiety via SCID or who have a HADS Anxiety score of eight (8) or higher will be eligible for study participation. Once it is determined that participants meet study eligibility criteria, participants will complete or undergo additional assessments of anxiety and depression, quality of life and functional status, described above. The primary caregivers will complete the HADS. The investigators will also provide participants with daily pain and medication diaries and instructions on how to complete them. Participants will begin completing daily pain and medication diaries starting after baseline analysis.

Randomized blinded Study phase

Randomization

Upon enrollment into the study, participants will be assigned to one of two conditions, active placebo (4 mg psilocybin) or full experimental intervention (25 mg psilocybin). Active placebo in this study is a low dose of the investigational drug that will not produce the unique effects of psilocybin. Participants have a 66% chance of assignment to the full experimental intervention, with six of nine participants will be assigned to receive the full experimental intervention and three will be assigned to receive active placebo. The internal review committee coordinator at the study site will generate and maintain the randomization code and procedure. Condition assignment will be maintained from study enrollment up through the course of the study, as there is no crossover design. If there is an adverse event or other emergency requiring knowledge of participant's condition assignment, as when pharmacological intervention is necessary, the blind may be broken for an individual participant.

Introductory Psychotherapy Session (Visits #4 and #4.5)

Psychotherapy

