If at least four participants complete measures during the follow-up two months after the second experimental or open-label psilocybin-assisted therapy session, then the investigators will perform separate repeated-measures ANOVAs on the anxiety, depression, quality of life and spirituality scores listed above, with p. set at 0.05. The investigators are chiefly interested in differences between baseline and two-month follow-up scores. If a sufficient number of participants complete pain measures on the date of the two-month follow-up session, then the investigators will perform a t-test to compare VAS pain ratings on the day of the two-month follow-up with the average pre-psilocybin pain rating.

Given that only three participants will be eligible for the open-label phase of the study, the investigators do not plan to perform formal comparisons between anxiety, depression, spirituality or quality of life across the randomized and open-label study phases. However, the investigators will perform informal observations and present descriptive statistics for all outcome variables two weeks after the second open-label psilocybin-assisted session.

Before analyzing differences between degree of mystical experiences or changes in spiritual identity for active placebo and experimental dose participants, the investigators will first perform a matched-sample t test to determine whether there were significant differences between mystical experience (SCQ) and self-concept boundary/spiritual identity (SELF) scores measured after each of the two psilocybin-assisted sessions. If there are no significant differences between SCQ and SELF scores after the first and the second psilocybin session, then the investigators will compute the average between the two scores and employ the average SCQ and SELF score in nearly all subsequent analyses of these scores. Subsequent analyses will include an analysis of variance comparing SCQ and SELF scores in active placebo and full-dose participants, and correlational analyses of anxiety (HADS and STAI) and depression (HADS) scores as related to SCQ and SELF scores, with p. set at 0.05. The investigators may also compare

SCQ scores and NK cell counts made from blood sampled approximately 23 hours after each psilocybin-assisted session to see whether there are associations between presence and degree of mystical experience changes in immunological function.

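### Tukey's test, the only follow-up named for a significant interaction, does not suit a two-by-two design with time repeated; report the difference in change and paired within-arm changes instead

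*Protocol*

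**What the plan says.** All of this is in the protocol; no SAP was available for this review.

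- **Model (Data Analysis).** The primary ANOVA compares the two doses between people and enters "time of administration (baseline versus two weeks after the second experimental psilocybin-assisted session) as a repeated measure". This gives two conditions by two times.
- **Follow-up (Data Analysis).** "The investigators will perform post-hoc tests (as Tukey's test) on any statistically significant interactions". No other follow-up method is named, and neither the error term nor the set of pairs is given.
- **Level (Data Analysis).** "Probability of rejecting the null hypothesis will be set at 0.05". The same paragraph declines Bonferroni corrections across the anxiety measures because the study is a small pilot.
- **Primary outcome (Assessments and Measures).** "The primary outcome measure for this study will be the HADS anxiety score". It is analysed with this model, so the follow-up sentence covers it, along with every other outcome in the model.
- **Allocation (Randomization).** "six of nine participants will be assigned to receive the full experimental intervention and three will be assigned to receive active placebo".
- **Pairing elsewhere (Data Analysis).** For the SCQ and SELF scores after the two sessions, "the investigators will first perform a matched-sample t test to determine whether there were significant differences".

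**The concern.** With two arms and two times, the interaction has one degree of freedom and equals the between-arm difference in mean change. Once it is significant there is nothing left to locate by testing every pair of cells. A reader needs the size of that difference and the change in each arm.

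Ordinary Tukey (Tukey-Kramer for 6 versus 3) supplies neither well. It uses one error variance pooled over four groups taken as independent, so it ignores the within-person correlation in the baseline to two-week comparison. It also corrects for six pairs, two of which set one arm's baseline against the other arm's follow-up and answer no useful question.

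An analyst who takes the named example at face value could report a significant difference in change and then state that no cells differ. The intervals on the within-arm changes would also be too wide.

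**Working it through.** **Inputs.** From the protocol: 6 and 3 participants, two times, level 0.05, effect 0.6 (Statistical Power, which takes 0.4 to 0.7 as plausible). Assumed, because the protocol does not give them: SD of 1 at each time, correlation ρ between baseline and two-week scores of 0.3 to 0.7, and the amount of change in the control arm.

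**1. Reproduce the protocol's power.** For a two-sample t test with 7 df, two-sided, the noncentrality is 0.6/√(1/6 + 1/3) = 0.6/0.707 = 0.849. Power is 0.1143, as stated. At ρ = 0.5 the SD of a change score is √(2(1 − 0.5)) = 1, so this is also the power of the interaction test for a 0.6 SD difference in change.

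**2. Standard error of the 25 mg change.**
- Cells taken as independent: √(2/6) = 0.577 SD.
- Paired: √(2(1 − ρ)/6), which is 0.408 SD at ρ = 0.5.
- The ratio is 1/√(1 − ρ): 1.20 at ρ = 0.3, 1.41 at 0.5 and 1.83 at 0.7. The independent-cell error is therefore 20%, 41% and 83% too wide.

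**3. Change needed for significance in the 25 mg arm (ρ = 0.5, SDs at their true values).**
- Tukey with four means and 14 df has q = 4.11, so the threshold is (4.11/√2) × 0.577 = 1.68 SD.
- The paired contrast with 7 df has t = 2.365, so the threshold is 2.365 × 0.408 = 0.97 SD.

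**4. Share of significant interactions with no significant Tukey pair.** These come from simulated trials with normal scores and independent-cell Tukey-Kramer over all six pairs. Repeat runs agree to about one percentage point.

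| Difference in change | Common change in both arms | ρ = 0.3 | ρ = 0.5 | ρ = 0.7 |
|---|---|---|---|---|
| 0.6 SD | none | 66% | 75% | 84% |
| 1.0 SD | none | 49% | 58% | 70% |
| 1.5 SD | none | 24% | 31% | 41% |
| 0.6 SD | 0.5 SD | 42% | 51% | 62% |
| 1.0 SD | 0.5 SD | 22% | 29% | 38% |

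**5. Detection of the 25 mg change after a significant interaction (ρ = 0.5, controls unchanged).** At 0.6 SD Tukey finds it in about 10% of cases. The paired contrast finds it in about 57%, even when held to 0.025. At 1.0 SD the figures are 28% and 81%.

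**6. Would another error term rescue the all-pairs test?** Only in part, because no single error suits all six pairs. For 25 mg versus 4 mg at one visit with ρ = 0.5, the within-subject error gives √((1 − 0.5)(1/6 + 1/3)) = 0.50 SD. The correct value is √(1/6 + 1/3) = 0.707 SD. The between-person error is too wide within arms, and the within-subject error is too narrow between them.

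**The case against.** The protocol does not say that the scores are handled as independent. In its usage the word before Tukey's name means 'such as', so the test is an example. Time is declared a repeated measure, the matched-sample test for SCQ and SELF shows that the authors recognise pairing, and Tukey comparisons can be run with the within-subject error. The error term of a post-hoc contrast is commonly left to a SAP. All of this stands. A reader might infer that the plan commits to an independence assumption, and the document does not support that. What remains is that the one method named is an all-pairs procedure whose ordinary form ignores the pairing, and that step 6 shows no error term makes it fit all six pairs.

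The protocol also leaves room for improvement in the control arm. Risks of Active Placebo dose of Psilocybin expects less anxiety reduction there than with the full dose, which is not the same as none, and Risk/Benefits Analysis gives these participants up to four non-drug sessions plus therapy during dosing. With common improvement the loss is smaller, as the table shows.

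Part of the loss comes from having nine people. Tukey with within-subject error, limited to within-arm pairs, still finds nothing in 43% to 61% of significant interactions at 0.6 SD for correlations up to 0.7, with controls unchanged.

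Finally, the step runs only after a significant interaction. Over all trials the loss at ρ = 0.5 is therefore about 11.4% × (57% − 10%) = 5 percentage points at 0.6 SD, and about 23.2% × (81% − 28%) = 12 points at 1.0 SD. Power for the post-hoc contrast calculated without that gate would overstate the loss.

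**Conclusion.** The point holds as a poor choice of named follow-up method. Ordinary Tukey on these four cells makes the standard error of the 25 mg change 20% to 83% too wide for correlations of 0.3 to 0.7, and it spreads the correction over six pairs when one contrast is the treatment effect. Under an unchanged control arm and the protocol's 0.6 SD, about two thirds to five sixths of significant interactions would show no significant pair.

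Two stronger readings are not supported. One is that most real interactions would end this way in general: that depends on the correlation, the effect size and the control-arm change, and it fails at 1.5 SD for every correlation tabulated. The other is that the primary result would be lost or contradicted. The interaction test is valid whatever the follow-up shows, and an absence of significant pairs does not overturn it. The ordinary Tukey error is conservative for within-arm change, so no false claim of efficacy follows from it. The harm is confined to explaining and reporting a significant result.

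**What to change.** Replace the follow-up sentence in Data Analysis with:

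> The condition-by-time interaction is the treatment effect and will be reported as the between-arm difference in mean change (25 mg minus 4 mg) with its 95% confidence interval. The mean change within each arm will be reported with a 95% confidence interval using the within-subject (paired) error term. All-pairs tests such as Tukey's will not be used.

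Apply it to every outcome analysed with this model. No Bonferroni adjustment is added, in keeping with the protocol's decision not to use one for the anxiety measures. The within-arm intervals describe change in each arm; the evidence on treatment remains the between-arm difference.

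The cost is one replaced passage of analysis wording, with no new data, visits or patients. The small downside is that the other pairs of cell means are not formally tested.
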